A repeated measures analysis will also be conducted in which changes from baseline in hourly mean values of SBP will be analyzed to test whether each dose of lasmiditan (100 mg, 200 mg) is noninferior to placebo at each time point (hour), assuming a noninferiority margin of 10 mmHg. A repeated measures linear mixed-effects model with baseline as a covariate, fixed effects for time point, treatment, period, treatment sequence, and the treatment by time point interaction, and a random effect for subject will be used to conduct the tests at a 1-sided significance level of 0.05. At each time point, LS means and treatment differences (lasmiditan 200 mg – placebo, lasmiditan 100 mg – placebo) will be calculated and presented with their corresponding 95% CIs, from which noninferiority of lasmiditan (100 mg, 200 mg) to placebo will be determined if the upper confidence limit is less than 10 mmHg.

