## 9.4 Cardiovascular Assessment

### 9.4.1 Cardiovascular Analysis

The primary parameter for the cardiovascular analyses will be peak hourly mean values of SBP, and will be determined using ambulatory blood pressure monitoring (ABPM). For each subject, the mean SBP value will be calculated for each hour within the dosing period. The highest mean value across the 24 calculated means will be considered the peak hourly mean value. Baseline value will be defined as the mean value during the 2 hours pre-dose for each period.

Additional analysis will be performed if warranted upon review of the data.

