### 9.4.2 Cardiovascular Statistical Methodology

Observed values, as well as change from baseline, for all cardiovascular parameters (including peak hourly mean SBP and mean hourly SBP values), will be listed and summarized by treatment using descriptive statistics. Mean hourly SBP values will be plotted over time, together with changes from baseline. In addition, mean hourly SBP and peak hourly mean SBP values will be plotted against plasma concentrations of lasmiditan to explore the relationship between PK and cardiovascular effects.

As a primary analysis, changes from baseline in peak hourly mean values of SBP will be analyzed to test whether each dose of lasmiditan (100 mg, 200 mg) is non-inferior to placebo, assuming a non-inferiority margin of 10 mmHg. Specifically, these changes from baseline will be analyzed to test the null hypothesis that the difference in mean baseline change between lasmiditan at each dose and placebo is at least 10 mmHg versus the alternative hypothesis that this difference is less than 10 mmHg.

A linear mixed-effects model with baseline as a covariate, fixed effects for treatment, period (1, 2, or 3), and treatment sequence, and a random effect for subject will be used to test the hypotheses at a 1-sided significance level of 0.05. Least squares (LS) means and treatment differences (lasmiditan 200 mg – placebo, lasmiditan 100 mg – placebo) will be calculated and presented with their corresponding 95% confidence intervals (CIs).

An example of the SAS code that will be used is as follows:

```
proc mixed data=xxx;
  class trtmnt period sequence subject;
  model cardiochg = baseline trtmnt period sequence / alpha=0.05 cl ddfm=kr;
  random subject;
  lsmeans trtmnt;
  lsestimate trtmnt 'Ltn100 - Placebo' 1 0 -1 / lower testvalue=10 cl alpha=0.05;
  lsestimate trtmnt 'Ltn200 - Placebo' 0 1 -1 / lower testvalue=10 cl alpha=0.05;
run;
```

where cardiochg is the change from baseline in peak hourly mean values of SBP, trtmnt is the treatment, and seq is the treatment sequence.

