The following gatekeeping procedure will be used to adjust for multiplicity when conducting the hypothesis tests. The null hypothesis that the difference in mean baseline change between lasmiditan 100 mg and placebo is at least 10 mmHg will first be tested against the alternative hypothesis that this difference is less than 10 mmHg. If the p-value for this test is less than 0.05, then there is significant evidence that lasmiditan 100 mg is non-inferior to placebo and these hypotheses will be re-tested using lasmiditan 200 mg. Otherwise, if the p-value is at least 0.05, then there is no significant evidence that lasmiditan 100 mg is non-inferior to placebo, in which case the null and alternative hypotheses will not be re-tested using lasmiditan 200 mg.

A sensitivity analysis will be performed on subjects who complete all 3 dosing periods. In addition, sensitivity analyses will be conducted where baseline value is the mean SBP value during the 1 hour pre-dose for each period. These analyses will be performed separately on subjects who complete at least 1 dosing period and on subjects who complete all 3 dosing periods. The same mixed-effects model as that was used in the primary analysis will be implemented.

A repeated measures analysis will also be conducted in which changes from baseline in hourly mean values of SBP will be analyzed to test whether each dose of lasmiditan (100 mg, 200 mg) is non-inferior to placebo at each time point (hour), assuming a non-inferiority margin of 10 mmHg. A repeated measures linear mixed-effects model with baseline as a covariate, fixed effects for time point, treatment, period, treatment sequence, and the treatment by time point interaction, and a random effect for subject will be used to conduct the tests at a 1-sided significance level of 0.05. An unstructured covariance structure will be applied. If the model fails to converge, alternative structures shall be examined using Akaike's criteria. At each time point, LS means and treatment differences (lasmiditan 200 mg – placebo, lasmiditan 100 mg - placebo) will be calculated and presented with their corresponding 95% CIs, from which non-inferiority of lasmiditan (100 mg, 200 mg) to placebo will be determined if the upper confidence limit is less than 10 mmHg.

An example of the SAS code that will be used is as follows:

```
proc mixed data=xxx;
  class trtmnt time period seq subject;
  model cardiochg = base time trtmnt period seq trtmnt*time / alpha=0.05 cl ddfm=kr;

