  repeated time / type=un subject=subject;
  random subject;
  lsmeans trtmnt*time / alpha=0.05 cl pdiff=controll('reftrt');
run;
```

where cardiochg is the change from baseline in hourly mean values of SBP, trtmnt is the treatment, seq is the treatment sequence, and reftrt is the reference treatment of the comparison.

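### The example code for the hourly SBP model omits period from the residual block, so the covariance matrix is singular for every subject with two or more periods, and its LSMEANS line cannot give the within-hour contrasts

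*SAP*

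**What the plan says.** The study has three periods per subject (SAP 5). In each period SAP 9.4.1 forms hourly means and then takes the peak: "The highest mean value across the 24 calculated means will be considered the peak hourly mean value".

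Besides the primary peak analysis, Protocol 10.3.3.2 and SAP 9.4.2 plan an hourly model. The protocol gives it "fixed effects for time point, treatment, period, treatment sequence, and the treatment by time point interaction, and a random effect for subject", and the SAP repeats this. The SAP adds two sentences on covariance: "An unstructured covariance structure will be applied", and "If the model fails to converge, alternative structures shall be examined using Akaike's criteria". Results are asked for hour by hour ("At each time point, LS means and treatment differences"), for each dose against placebo, with 95% confidence intervals whose upper limit is compared with 10 mmHg.

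The example code has period as a fixed effect and a random subject intercept. Its residual statement is "repeated time / type=un subject=subject". The differences come from "lsmeans trtmnt*time / alpha=0.05 cl pdiff=controll('reftrt" (the line continues to its closing bracket), and the SAP explains the placeholder as the reference treatment only.

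**The concern.** A REPEATED statement needs an index that identifies each observation within its block. Here the index is hour and the block is the subject, but a completer contributes each hour three times, once per period. The code therefore treats the 3 a.m. mean in period 1 and the 3 a.m. mean in period 2 as having the same residual. The random subject intercept cannot separate them, because it too is shared across periods.

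This is the plan's only inferential analysis by hour. The study was prompted by a transient rise between 60 and 90 minutes postdose in Study LAHA (Protocol 3.1). The primary parameter is a maximum over 24 hours and does not locate an effect in time. If the hourly model cannot be fitted as written, the residual block will be chosen once it fails, with data in hand. SAP 3 intends the plan to be signed off before first dosing.

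The LSMEANS line is a second, smaller mismatch. A treatment-by-hour cell is identified by a treatment and an hour, and the line supplies only a treatment.

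**Working it through.** The plan gives no figure for this model. Its one design figure, at least 90% power for the primary test (SAP 7), is reproduced but does not bear on this point. With 6.0 mmHg read as the per-period SD, SE = 6√2/√30 = 1.549 and power = Φ(5/1.549 − 1.645) = 94.3%. Read as the SD of the difference, it gives 99.8%.

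**Inputs**
- 3 periods per subject (SAP 5)
- 24 hourly means per period (SAP 9.4.1)
- 30 completers, up to 36 enrolled (SAP 7)
- repeated index hour, block subject, random subject intercept (SAP 9.4.2 example code)

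Let Σ be the 24 × 24 residual covariance over hours, τ² the subject variance, J an all-ones matrix and I the identity.

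**Step 1: smallest case, one hour in two periods, residual variance σ².**
- As coded, all four elements of V equal σ² + τ², so its determinant is 0.
- With subject-by-period blocks, the diagonal is σ² + τ² and the off-diagonal τ². The determinant is σ⁴ + 2σ²τ², which is positive.
- The same-hour difference between periods has variance 0 as coded, against 2σ² with the corrected block. The documents do not give σ². Assuming σ² = 36 (borrowing the 6.0 mmHg SD, which describes another quantity) gives 72 mmHg²; assuming σ² = 64 gives 128 mmHg². What matters is zero against non-zero.

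**Step 2: full size, P periods.**
- As coded: R = J_P ⊗ Σ and V = J_P ⊗ (Σ + τ²J₂₄). J_P has rank 1, so both have rank 24 whatever P is. Also, τ² enters only through Σ + τ²J₂₄, so it cannot be separated from Σ.
- Subject-by-period: R = I_P ⊗ Σ and V = I_P ⊗ Σ + τ²J, both of full rank.

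Numerical check with an arbitrary positive definite Σ (the ranks do not depend on it):

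| Periods | Rows | Rank of R and V, as coded | Rank, subject-by-period |
|---|---|---|---|
| 1 | 24 | 24 | 24 |
| 2 | 48 | 24 | 48 |
| 3 | 72 | 24 | 72 |

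A completer thus has 72 − 24 = 48 zero eigenvalues. One hour shared by two periods is enough: 25 rows, rank 24. Σ itself is not singular; the repetition of its rows causes the fault.

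**Step 3: does the fallback help?** Hour-indexed AR(1) and compound symmetry within the subject block also gave rank 24 of 72. Changing the structure while keeping block and index does not restore rank.

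**Step 4: could the time variable mean 72 distinct period-hours?** An unstructured matrix would then need 72 × 73/2 = 2,628 parameters from at most 36 subjects. The treatment-by-time term would also no longer compare treatments at the same hour, as the text requires.

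**Step 5: contrasts.** The text requires 2 doses × 24 hours = 48. There are 3 × 24 = 72 treatment-by-hour cells. One control cell gives 71 differences, of which only 2 fall within its own hour.

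**Step 6: is the corrected model estimable?** It has 24 × 25/2 = 300 covariance parameters and 30 × 3 = 90 blocks from completers. In simulated data under assumed variances, correlations and dropout, with no missing hours, a REML fit by EM converged in 20 of 20 data sets in each of three scenarios. PROC MIXED was not run, so its convergence with 300 parameters is not established.

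**The case against.** The strongest defence is that the fault lies in illustrative code and not in the stated method. The SAP calls the code an example and uses placeholders, and its text is compatible with a valid model. The failure should be obvious when the code is run, so it would not silently distort a result. SAP 3 also requires substantial deviations to be agreed and identified in the study report. All of this stands, and it is why the point is minor. It does not remove the point: the text names no residual block, so this line is the only place where one is stated, and it is wrong. Documenting a later choice is not the same as specifying it beforehand.

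A second defence is that the Akaike clause does not limit the alternatives to hour-indexed structures. That is fair: a period-by-hour structure would work. None is named, however, so repair is possible but not assured.

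Third, the contrasts are fully stated in the text, so an analyst who follows the text would not report the wrong ones. That also stands; the LSMEANS line is a coding slip.

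Finally, a subject-by-period block is not the only valid choice. With a random subject intercept it assumes constant covariance between periods. It is the simplest repair that keeps the planned unstructured matrix over hours.

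**Conclusion.** The concern holds and is minor. Followed as written, the hourly model has no valid likelihood for any subject with two or three periods, including all 30 planned completers. The result is algebraic and rests on one condition: that at least one hour is observed in more than one of a subject's periods. With 24 planned hourly means per period this is close to certain. Single-period subjects are unaffected. The LSMEANS line does not match the 48 within-hour differences in the text.

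The primary model has no REPEATED statement. The primary test, gatekeeping, sensitivity analyses, power and descriptive summaries are therefore untouched.

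**What to change.** 1. In the hourly example code, change the block option to `subject=subject*period` and keep the random subject intercept. Period is already in that code's CLASS statement.
2. State in SAP 9.4.2 that the residual block is subject-by-period and that it also applies to any structure tried under the Akaike clause. Name the simpler structures in advance, for example Toeplitz and then AR(1), because 300 parameters may still not converge.
3. Replace the LSMEANS line with 100 mg minus placebo and 200 mg minus placebo at each hour. The primary code shows a usable pattern ("lsestimate trtmnt 'Ltn100 - Placebo' 1 0 -1 / lower testvalue=10 cl alpha=0.05"), but its coefficients must be rewritten for the treatment-by-hour term. Report the two-sided 95% intervals that the text requires, with the upper limit compared with 10 mmHg. The same paragraph also cites a one-sided 0.05 level, while a two-sided 95% limit corresponds to 0.025 one-sided; the SAP should say which governs.

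The cost is two code lines and one or two sentences of text for the block, fallback and contrasts, plus a clause on the level. There is no cost in data or to subjects.

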## **9.5 Safety and Tolerability Assessments**

### **9.5.1 Adverse events**

Where changes in severity are recorded in the Case Report Form (CRF), each separate severity of the AE will be reported in the listings, only the most severe will be used in the summary tables. A pre-existing condition is defined as an AE that starts before the subject has provided written informed consent and is ongoing at consent. A non-treatment emergent AE is defined as an AE which starts after informed consent but prior to dosing. A treatment-emergent AE is defined as an AE which occurs postdose or which is present prior to dosing and becomes more severe postdose.

All AEs will be listed. Treatment-emergent AEs will be summarized by treatment, severity and relationship to the study drug. The frequency (the number of AEs, the number of subjects experiencing an AE and the percentage of subjects experiencing an AE) of treatment-emergent AEs will be summarized by treatment, Medical Dictionary for Regulatory Activities (MedDRA) version 20.0 system organ class and preferred term. The summary and frequency AE tables will be presented for all causalities and those considered related to the study drug. Any serious AEs will be tabulated.

### **9.5.2 Concomitant medication**

Concomitant medication will be coded using the WHO drug dictionary (Version March 2017). Concomitant medication will be listed.

### **9.5.3 Clinical laboratory parameters**

All clinical chemistry, hematology and urinalysis data will be listed. Additionally clinical chemistry, hematology and urinalysis data outside the reference ranges will be listed.

Values for any clinical chemistry, hematology and urinalysis values outside the reference ranges will be flagged on the individual subject data listings.

#### **9.5.4 Vital signs**

Supine vital signs data will be summarized by treatment together with changes from baseline, where baseline is defined as predose of each period. Figures of supine mean vital signs and mean changes from baseline profiles by treatment will be presented by treatment.

Furthermore, values for individual subjects will be listed.

#### **9.5.5 Electrocardiogram (ECG)**

For each subject, ECGs will be performed for safety purposes only, and will not be reported.

#### **9.5.6 Hepatic Monitoring**

If a subject experiences elevated alanine aminotransferase (ALT)  $\geq 3 \times$  upper limit of normal (ULN), alkaline phosphatase (ALP)  $\geq 2 \times$  ULN, or elevated total bilirubin (TBL)  $\geq 2 \times$  ULN, liver tests will be performed to confirm the abnormality.

The subjects' liver disease history and associated person liver disease history data will be listed. Any concomitant medication of acetaminophen/paracetamol will be listed. Results from any hepatic monitoring procedures, such as a magnetic resonance elastography (MRE) scan, and a biopsy assessment will be listed, if performed.

Hepatic risk factor assessment data will be listed. Liver related signs and symptoms data will be summarized by treatment and listed. Alcohol and recreational drug use data will also be listed.

All hepatic chemistry, hematology, coagulation, and serology data will be listed. Values outside the reference ranges will be flagged on the individual subject data listings.

#### **9.5.7 Columbia Suicide Severity Rating Scale (C-SSRS)**

Data from the C-SSRS and self-harm questionnaire will be listed for individual subjects.

#### **9.5.8 Other assessments**

All other safety assessments not detailed in this section will be listed but not summarized or statistically analysed.

#### **9.5.9 Safety and Tolerability Statistical Methodology**

No inferential statistical analyses are planned.

### **10. INTERIM ANALYSES**

No interim statistical analyses are planned.

### **11. CHANGES FROM THE PROTOCOL SPECIFIED STATISTICAL ANALYSES**

There were no changes from the protocol specified statistical analyses.

---

## 13. DATA PRESENTATION

### 13.1 Derived Parameters

Individual derived parameters (e.g. PK parameters) and appropriate summary statistics will be reported to three significant figures. Observed concentration data, e.g.  $C_{max}$ , should be reported as received. Observed time data, e.g.  $t_{max}$ , should be reported as received. N and percentage values should be reported as whole numbers. Median values should be treated as an observed parameter and reported to the same number of decimal places as minimum and maximum values.

### 13.2 Missing Data

Missing data will not be displayed in listings.

### 13.3 Insufficient Data for Presentation

Some of the TFLs may not have sufficient numbers of subjects or data for presentation. If this occurs, the blank TFL shell will be presented with a message printed in the centre of the table, such as, "No serious adverse events occurred for this study."

Leo Document ID = 7fdb12ee-585f-4303-baa1-52675bd3e9cc

Approver: PPD

Approval Date & Time: 07-Feb-2018 19:33:38 GMT

Signature meaning: Approved

Approver: PPD

Approval Date & Time: 07-Feb-2018 20:09:26 GMT

Signature meaning: Approved

Approver: PPD

Approval Date & Time: 07-Feb-2018 21:31:07 GMT

Signature meaning: Approved

Approver: PPD

Approval Date & Time: 08-Feb-2018 09:11:55 GMT

Signature meaning: Approved
